7.3. Laboratory Evaluations

All continuous laboratory parameters in hematology and clinical chemistry will be summarized descriptively by absolute value at each visit by treatment group, together with the corresponding changes from baseline. All parameters will be summarized in SI units. Hemoglobin and Hematocrit will also be summarized in Conventional units.

The number and percentage of subjects with laboratory measurements outside of the central laboratory normal range will also be summarized by treatment group and visit. Shift tables from baseline to maximum post-baseline value, to minimum post-baseline value, last post-

baseline value, and at each post-baseline visit will be provided for hematology and chemistry parameters to display low, normal, high, and missing values by treatment group in a 3-by-3 contingency table. Denominators for percentages will be the number of subjects with non-missing data at the specific assessment and baseline.

A sample for the urinalysis and urine culture will be sent to the central laboratory only if the urine dipstick performed at the site tests positive for the presence of leukocytes, nitrites, or blood cells. Central urinalysis data will only be presented in the listing.

Any data outside the central laboratory normal reference ranges will be explicitly noted on the listings that are produced.

7.4. Vital Signs

Vital sign data including blood pressure, pulse rate, respiration rate, and body temperature will be collected at all study visits except for the telephone follow-up visits. Height will be measured at Screening only.

For all parameters, absolute values and change from baseline will be presented for scheduled visits using descriptive statistics for continuous variables. In addition, the maximum post-baseline, change from baseline to the maximum post-baseline, and change from baseline to the last post-baseline value will be summarized for each of the vital signs.

A by-subject listing, sorted by treatment and subject identifier, will be presented including all vital sign results (scheduled or unscheduled).

7.5. ECG

12-Lead ECG data will be collected at the screening visit and at Week 2, 12, and 24 visits. For all parameters, absolute values and change from baseline will be presented for scheduled visits using descriptive statistics for continuous variables. The evaluation result will be summarized at each visit as well.

A by-subject listing, sorted by treatment and subject identifier, will be presented including all ECG results (scheduled or unscheduled).

7.6. Physical Examination

Physical examination data will be collected at Screening and Week 24. Shift tables (normal, abnormal, not done) of baseline versus the last observation post-baseline [normal, abnormal (same as baseline), abnormal (new or aggravated), not done] may be generated, presenting the assessment for each component of the physical examination separately. Listing of abnormal results will be produced.

7.7. PVR

The volume of urine that remains in the bladder after voiding is an objective measurement that may serve as a proxy for impaired ability to void. Absolute values and change from baseline will be presented for scheduled visits using descriptive statistics for PVR measurements. In addition, the maximum post-baseline, change from baseline to the maximum post-baseline, and change from baseline to the last post-baseline value will be summarized. The maximum and the last post-baseline value will not use the visit windows rules and any non-missing post-baseline values will be used for the derivation. A categorical summary will be based on the following levels:

- < 100 mL
- ≥ 100 and < 200 mL
- ≥ 200 and < 350 mL
- ≥ 350 mL

All PVR measurements will be listed.

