Currently, the predominant class of drugs used to treat OAB is antimuscarinics. The clinical utility of antimuscarinics is limited by their modest efficacy and poor tolerability due to mechanism-based side effects including dry mouth and constipation. In addition to poor tolerability and modest efficacy, a recent body of literature suggests that chronic use of anticholinergics is associated with cognitive impairment and dementia [Risacher, 2016; Gray, 2015]. Mirabegron (Myrbetriq®; Astellas Pharma US, Inc), a β3-agonist and smooth muscle relaxer, is currently approved in multiple countries for the treatment of OAB [Nitti, 2013]. The reported adverse effects with mirabegron were similar to antimuscarinics, but with a lower incidence of dry mouth compared with tolterodine, an antimuscarinic. However, the effects of mirabegron on the cardiovascular system, pharmacokinetic interactions with other drugs, and increased incidence of new malignant events will require careful evaluation in the near future [Sacco, 2012]. In addition, BOTOX® (onabotulinumtoxinA), a neurotoxin which inhibits muscle contraction by blocking neuromuscular transmission through decreased acetylcholine release, has been approved for the treatment of neurogenic and idiopathic OAB (since 2011 and 2012, respectively). BOTOX is administered via multiple intradetrusor injections into the bladder wall about every 6 months. BOTOX has been associated with urinary tract infections (UTIs), dysuria, and urinary retention. Other side effects are consistent with the mechanism of action of botulinum toxin and may include asthenia, generalized muscle weakness, diplopia, ptosis, dysphagia, dysphonia, dysarthria, urinary incontinence, and breathing

difficulties. These symptoms have been reported hours to weeks after injection [BOTOX Package Insert, 2018].

A major problem with currently available OAB treatments is that even when these drugs have documented efficacy, treatment is still limited by their side effects. There is a significant unmet need for the treatment of OAB with agents with novel mechanisms of action and a well-tolerated safety profile.

*URO-902*

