### **6.9.1. Prohibited Drugs and Washout**

Section 10.7 provides a list of medications prohibited before the study and during the study (until Week 24) and the associated washout periods. If there is a clinical indication for any therapy that is specifically prohibited during the study, discontinuation from the study may be required. The investigator should discuss any questions regarding this with the Sponsor's designated Medical Monitor. The final decision on any supportive therapy rests with the investigator and/or the subject's primary physician. However, the decision to continue the subject in the study requires the mutual agreement of the investigator and the Sponsor's designated Medical Monitor. Consult the Sponsor's designated Medical Monitor if there is any uncertainty regarding subject use of a particular drug or drug class.

Starting at Week 24 and after, the OAB treatments listed in [Section 10.7](#) are no longer prohibited and can be prescribed to a subject upon her request and in accordance with the investigator's clinical judgment. See [Section 6.9.2](#) for details.

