4.2.2. Reporting Conventions

General rules

In general, all collected safety data, any derived efficacy parameters from the bladder diary, questionnaire data, and urodynamic data will be presented in subject data listings. Listings will be ordered by treatment, subject number, and assessment week or event date. The treatment group presented in listings will be based on the planned assignment for efficacy endpoints and actual assignment for safety endpoints.

Summary tables will be provided for all randomized subjects. All demographic and baseline data will be presented by treatment arm and overall, unless otherwise specified. Bladder diary, questionnaire, urodynamic data, and safety data will be presented by treatment arm only. In general, continuous variables will be summarized to include the population sample size (N), number of subjects with available data (n), arithmetic mean, standard deviation (SD), median, minimum, Q1, Q3 and maximum values. Categorical variables will be summarized by the population size (N), number of subjects with available data (n), number of subjects in each category, and the percentage of subjects in each category. Unless otherwise noted, the denominator to determine the percentage of subjects in each category will be based on the number of subjects with available data (n) in the analysis set of interest. Selective ordinal data may be summarized using both descriptive statistics as well as counts and percentages of subjects in each category, as appropriate.

The data analyses will be conducted using the SAS® System (SAS Institute Inc., Cary, NC) version 9.3 or above. The eClinical Solutions' standard operating procedures will be followed for the validation of all SAS programs and outputs.

Formats

Numeric data will be reported at the precision collected on the electronic case report form (eCRF). The reported precision from non eCRF sources may be adjusted to a clinically interpretable number or decimal places.

Unscheduled Visits

Unscheduled visits will be assigned to an analysis visit using the all-inclusive windows defined in [Section 4.2.4](#). If multiple assessments are done in the same visit, the selection rule in [Section 4.2.4](#) will apply. All assessments at unscheduled visits will be included for deriving last post-baseline or maximum value post-baseline and in the data listings.

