7.2. Adverse Events

Adverse events (AEs) will be coded using MedDRA version 22.1. or later.

All reported AEs (whether treatment emergent or not) will be included in by-subject AE listings. Sorting will be by treatment, subject, date of event, SOC, PT and then verbatim description.

An AE will be considered a treatment emergent adverse event (TEAE) if it begins or worsens in severity after initial exposure of the study treatment through 48 weeks after treatment administration or the date of the initiation of another OAB medication, investigational agent or surgical intervention, whichever occurs first. The determination of "48 weeks" will be based on the study day of the AE start date instead of the visit date of the Week 48 visit. The OAB medication will be determined based on the checkbox "Is this an additional OAB medication"

on the concomitant medication CRF. After data are collected and reviewed by the clinical team, a blinded list of investigational agents and surgical interventions will be provided to the programming team prior to database lock to determine which AEs should no longer be considered treatment emergent due to possible confounding effects. Partial AE start dates will be imputed as detailed in [Section 4.2.3](#).

Summary tables will be based on TEAEs. The incidence of TEAEs will be presented using counts and percentages of subjects with TEAEs and tabulated by SOC and PT. SOC will be sorted in descending frequency and PT within SOC will be sorted by descending frequency based on the incidence of all subjects treated with URO-902 included in the summary. If a subject has multiple occurrences (start and stop) of an event associated with a specific SOC or PT within a SOC, a subject will only be counted once in the incidence count for the SOC or PT within SOC respectively.

An overall summary table of AEs by treatment group will be presented detailing the number and percentage of subjects, and number of events for the following categories:

- At least one TEAE;
- At least one Treatment-Related TEAE;
- At least one Grade ≥ 3 TEAE (Mild = Grade 1, Moderate = Grade 2, Severe = Grade 3, Life-Threatening = Grade 4, Death = Grade 5)
- At least one Grade ≥ 3 Treatment-Related TEAE;
- At least one Serious TEAE;
- At least one Serious Treatment-Related TEAE;
- At least one TEAE leading to Discontinuation from Study;
- At least one TEAE of Special Interest;
- At least one Treatment-Related TEAE of Special Interest

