7.8. Clean Intermittent Catheterization (CIC)

For subjects with CIC initiated, time from study drug injection to the start of CIC (in days) and length of CIC use (in days) will be summarized by treatment arms. If CIC is used more than once, the length will be summed together for summary purpose. No imputation will be done for CIC start and stop dates. All CIC information will be provided in the listing.

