9. CHANGE FROM ANALYSIS PLANNED IN PROTOCOL

[figure not shown]
Protocol section 9.3 defined analyses population. In the SAP [Section 3.1](#), safety (modified) population was removed.

Protocol section 3.2.1 defined exploratory efficacy endpoints. In the SAP [Section 1.1.1](#) and [Section 4.3.2](#) , ‘Nighttime voids’ was added as an exploratory efficacy endpoint.

In the SAP [Section 7.2](#) the definition of treatment-emergent adverse event was updated to include the additional OAB medication as the end of the treatment-emergent period in addition to the initiation of the investigational agent and/or surgical intervention.

In Protocol section 9.5.1 PGI-C change from baseline was analyzed using MMRM method. In the SAP section 4.3.3 and 6.2 the analysis method for PGI-C was changed to use the responder analysis with CMH method.

SAP added additional endpoint of proportion of subjects achieving $\geq 50\%$, $\geq 75\%$ and 100% reduction in average daily UI episodes.

Since no analysis plan is definitive especially for this exploratory study, we may perform additional data driven sensitivity analysis.

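### Maximum and last PVR and the CIC summaries have no cut-off at additional OAB treatment, although the adverse-event and diary rules do

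*SAP*

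**What the plan says.** SAP 7.7 takes the maximum and last post-baseline PVR outside the visit-window rules: "any non-missing post-baseline values will be used for the derivation". SAP 4.2.2 extends this to extra visits: "All assessments at unscheduled visits will be included for deriving last post-baseline or maximum value post-baseline". SAP 7.8 summarises CIC by arm: "For subjects with CIC initiated, time from study drug injection to the start of CIC (in days) and length of CIC use", with repeat episodes added together. None of the three mentions additional OAB treatment.

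Two other SAP rules do. SAP 7.2 ends the treatment-emergent period at 48 weeks "or the date of the initiation of another OAB medication, investigational agent or surgical intervention, whichever occurs first". SAP 4.3.2 leaves diaries collected after the first additional OAB treatment out of the endpoints. Adverse events that fall after the SAP 7.2 date are summarised in Table 14.3.1.14. The table list in SAP 11.1.1 has no PVR or CIC counterpart.

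The protocol shows how the two can diverge. From Week 24 the OAB treatments in Protocol 10.7, botulinum toxin among them, "are no longer prohibited and can be prescribed to a subject upon her request" (Protocol 6.9.1). Protocol 2.1 notes that "BOTOX has been associated with urinary tract infections (UTIs), dysuria, and urinary retention". Protocol 9.3 defined a safety population that left out subjects with additional OAB medication at or after Week 24; SAP 9 records that the "safety (modified) population was removed".

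**The concern.** Urinary retention is an adverse event of special interest (Protocol 8.5.6), and PVR and CIC are its measurable side. If another agent causes the retention, the SAP treats the event as confounded for adverse-event tables but not for maximum PVR, last PVR or CIC. The same subject is then handled in two ways, and the PVR and CIC results of her arm include an effect that study drug did not produce.

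The direction is not fixed. If additional treatment is more common on placebo, the placebo PVR and CIC results rise and the contrast with URO-902 narrows. If it is more common on URO-902, the contrast widens. Expected counts are small, so one subject can matter.

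**Working it through.** The plan states no figure on this point, so the check is mainly a tracing of rules.

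**1. One hypothetical subject through each rule.** After Week 24 she receives botulinum toxin recorded as additional OAB medication, has a PVR of 400 mL at an unscheduled visit, and starts CIC.

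- Adverse event: Protocol 8.5.6 records retention only with a raised PVR that needs catheterisation, so the event comes with PVR and catheterisation data. Under SAP 7.2 it is not treatment-emergent and goes to Table 14.3.1.14.
- Diaries: any later diary is excluded (SAP 4.3.2).
- Maximum PVR: 400 mL counts.
- Last PVR: the unscheduled value replaces the Week 24 value. Starting CIC triggers another PVR one week later (Protocol 8.4.5), which then becomes the last value.
- CIC: her start time, measured from the study injection, and her duration count.
- Arm: the treatment actually received (SAP 3.1.3).

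**2. When such values can arise.** After additional OAB treatment at or after Week 24, follow-up is for adverse events by telephone or virtual visit only (Protocol 6.9.2). The last PVR window in SAP Table 3 is Week 24. A later PVR therefore needs an unscheduled or CIC follow-up visit.

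OAB treatment before Week 24 is different. SAP 5.4.1 counts it whenever received, and Tables 14.1.5.3 and 14.1.5.5 are planned for it. The scheduled Week 24 or exit PVR, and possibly Week 12, would then follow the other treatment.

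**3. By-visit table.** The Week 24 PVR window is open from Day 149, but SAP 4.2.4 picks the record closest to Day 169. A Week 24 visit within its 7-day window is at most 7 days away. A Week 26 value falls on Day 26 × 7 + 1 = 183, which is 14 days away and does not displace it.

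**4. The two cut-off dates differ.** SAP 7.2 uses the checkbox for additional OAB medication, plus investigational agents and surgical interventions. SAP 4.3.2 uses additional OAB treatment, which under SAP 5.4.1 covers procedures as well. A non-surgical OAB procedure may not trigger the SAP 7.2 date.

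**5. Size for one subject, with 26 per group (Protocol 9.2).**

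- Mean maximum PVR: (400 − 50)/26 = 13.5 mL. Both PVR values are assumed.
- If the SAP 7.7 categories are applied to the maximum, which SAP 7.7 does not say: 1/26 = 3.8 percentage points in the top category.
- CIC: the summary covers only subjects who start CIC. With one such subject in an arm, she is the whole summary.

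**6. How often.** The documents give neither the share r who receive additional treatment nor the retention risk q among them. Both are assumed. Expected cases per arm = 26 × r × q; chance of at least one = 1 − (1 − rq)^26.

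| r | q | Expected per arm | At least one per arm | At least one in 78 |
|---|---|---|---|---|
| 10% | 2% | 0.05 | 5% | 15% |
| 30% | 5% | 0.39 | 33% | 69% |
| 50% | 10% | 1.30 | 74% | 98% |

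The last column uses 78 in place of 26. The width of the range shows that the documents cannot settle the frequency.

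**The case against.** The strongest reply is that little PVR data exists after permitted additional treatment, because none is scheduled. That stands and limits the size. It does not remove the problem: a retention event as the protocol defines it brings its own PVR and catheterisation data.

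OAB treatment before Week 24 is prohibited, may require discontinuation (Protocol 6.9.1), and may be a major deviation if the medical monitor has not approved it (SAP 3.2.1). Keeping scheduled measurements from such subjects is ordinary all-observed safety reporting. That is a fair defence of an all-observed table, but not of having only that table when adverse events are split.

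Safety is descriptive only (SAP 7), and PVR, CIC and additional OAB treatments are all listed, so a reader could trace one or two cases by hand. That is true and lowers the stakes.

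A reader might infer several stronger things that the documents do not support:

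- That the open-ended Week 24 window routinely brings later values into the by-visit table. The closest-to-target rule prevents this when a usable Week 24 value exists.
- That a URO-902 signal would be hidden. Values in the active arms do not change when placebo subjects receive other treatment, scheduled PVR normally precedes permitted treatment, and retention events are tabulated with the cut-off.
- That the event is lost. It moves to Table 14.3.1.14.
- That the percentage of subjects using CIC is distorted. SAP 7.8 plans time to start and duration, not an incidence percentage.
- That the dropped safety population would have given PVR and CIC tables free of other treatment. Protocol 9.5.2 left the choice of repeated tables to the SAP.

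**Conclusion.** The inconsistency is real and rests on the text alone: maximum PVR, last PVR and CIC have no cut-off at additional OAB treatment, while adverse events and diaries do, and the separate display covers adverse events only. Following the rules as written would attribute retention after another agent to the study-drug arm in some tables and not in others.

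The likely effect is limited to a few subjects and could fall on any arm. The 13.5 mL shift assumes 400 mL in place of 50 mL in one of 26 subjects. The frequency range rests on assumed rates. The point is worth correcting because correction is cheap and discards no data; it does not undermine the safety analysis as a whole.

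**What to change.** In SAP 7.7, derive the main maximum and last PVR, and any categories based on them, from values up to the first additional OAB treatment (medication or procedure), investigational agent or surgical intervention. State how this date relates to the SAP 7.2 date, whose OAB component covers medication only. Also state which PVR value the categories use.

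In SAP 7.8, classify each CIC episode by whether it started before or after that date, and keep the full duration of CIC that started before it. Cutting such an episode short could remove time that is due to study drug.

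Show all-observed and post-treatment PVR and CIC separately, parallel to Table 14.3.1.14.

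The cost is SAP wording, one date filter and one or two extra tables. The downside is slightly shorter follow-up in the main PVR summary for subjects who receive additional treatment; their later values remain visible in the separate display.

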7.8. Clean Intermittent Catheterization (CIC)

For subjects with CIC initiated, time from study drug injection to the start of CIC (in days) and length of CIC use (in days) will be summarized by treatment arms. If CIC is used more than once, the length will be summed together for summary purpose. No imputation will be done for CIC start and stop dates. All CIC information will be provided in the listing.

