##### *Initiation of Clean Intermittent Catheterization*

As described above in the PVR section, CIC should be initiated per protocol when one of the following criteria is fulfilled:

- PVR is  $\geq 350$  mL at any posttreatment visit, regardless of whether the subject reports associated symptoms
- PVR is  $\geq 200$  mL and  $< 350$  mL and the subject spontaneously reports associated symptoms (ie, voiding difficulties, sensation of bladder fullness) that in the opinion of the investigator requires CIC.

The following will occur when initiating CIC (for elevated PVR as described above):

1. CIC is implemented and the subject should be instructed to perform CIC using sterile, single-use catheters (which will be provided to the subject)
2. An adverse event of urinary retention is recorded
3. Central laboratory urine analysis and culture/sensitivity are performed as per routine requirements at each study visit
4. The subject will be seen for a follow-up visit 1 week later where the PVR, associated symptoms, central laboratory urine analysis and culture/sensitivity will be reassessed. The investigator will determine whether the subject can then be followed per protocol scheduled study visits or whether additional follow-up visits should occur.

Once CIC is initiated, the status of CIC use should be documented in the subject record at each visit (ie, use/nonuse).

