##### *Cessation of Clean Intermittent Catheterization*

CIC should be discontinued when the following criteria are fulfilled:

- the subject does not have any associated symptoms which in the opinion of the investigator require CIC AND

- the PVR is < 350 mL

The date of discontinuation of CIC should be documented. If the investigator deems that CIC should not be discontinued even though the above criteria are fulfilled, then this should be documented, and the reason given. Upon discontinuing CIC, the subject will be seen for a follow-up visit 1 week later where the PVR, associated symptoms, central laboratory urine analysis and culture/sensitivity will be reassessed. The investigator will determine whether the subject can then be followed at regularly scheduled study visits or whether additional follow-up visits should occur based on PVR and/or associated symptoms.

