4.2.3. Premature Withdrawal and Missing Data

If any missing data are present in diary data for any reasons, no imputation will be applied to derive responder. No explicit missing data imputation will be performed for change from baseline since a mixed model for repeated measures (MMRM) will be applied to change from baseline analysis. For responder analyses, subjects with missing assessments will be considered non-responders. Missing items from the questionnaires will be handled according to the respective measure instructions as described in [Section 4.3.3](#).

In general, missing safety data will not be imputed and only observed values will be analyzed.

If the relationship of an AE record (“Relationship to Study Treatment” on AE eCRF) is missing this AE will be considered “Probably Related” to the study treatment. If the AE severity is missing every effort should be made to acquire the information from the investigator. “Severe” will be assigned to a missing intensity for reporting purposes.

The general imputation rules of partial missing date for both AE and concomitant medication are detailed below:

Dates with missing the day of the year will adhere to the following conventions:

- The missing day of onset date will be set to:
 - First day of the month that the event occurred, if the onset YYYY-MM is after the YYYY-MM of the study treatment
 - The day of the study treatment, if the onset YYYY-MM is the same as YYYY-MM of the study treatment

- The date of informed consent, if the onset YYYY-MM is before the YYYY-MM of the study treatment.
- The missing day of end date will be set to:
 - The last day of the month of the occurrence. If the subject died in the same month, then set the imputed date as the death date.

Dates with missing both the day and month of the year will adhere to the following conventions:

- Missing day and month of onset date will be set to:
 - January 1 of the year of the onset, if the onset YYYY is after the YYYY of the study treatment
 - The date of the study treatment, if the onset YYYY is the same as YYYY of the study treatment
 - The date of informed consent, if the onset YYYY is before YYYY of the study treatment
- The missing date of end date will be set to:
 - December 31 of the year of occurrence. If the subject died in the same year, then set the imputed date as the death date.

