4.3.4. Study Day and Duration

Study day is relative to the start date of the double-blind treatment. This is used to describe the relative time of an event or assessment that happened during the study. The first day of the study is defined as the day a subject receives either URO-902 (24 or 48 mg) or placebo. There is no study Day 0 defined.

- For an event or assessment that occurred on or after the study treatment: Study day = Date of event or examination – date of study treatment + 1
- For an event or assessment that occurred prior to the study treatment: Study day = Date of event or examination – date of study treatment

A duration between any two dates (such as AE duration) expressed in days will be calculated using the following conventions: Duration = later date – earlier date + 1.

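### SAP 7.8 gives no rule for catheterisation still ongoing at last contact, so length of CIC use is understated if any subject has not stopped

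*SAP*

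**What the plan says.** SAP 7.8 covers subjects in whom CIC was started. It summarises time from injection to first use, and states that "length of CIC use (in days) will be summarized by treatment arms". For repeat use it says "If CIC is used more than once, the length will be summed together for summary purpose". It then says "No imputation will be done for CIC start and stop dates", and sends all CIC records to a listing. The output is Table 14.3.8 in SAP 11.1.1.

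Three other places bear on the calculation:

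- SAP 4.3.4 defines any duration in days as "Duration = later date – earlier date + 1".
- SAP 4.2.3 says "In general, missing safety data will not be imputed and only observed values will be analyzed". Its partial-date conventions are limited in scope: "The general imputation rules of partial missing date for both AE and concomitant medication are detailed below". CIC is not among them.
- Protocol 8.4.5 obtains the stop date when catheterisation ends: "The date of discontinuation of CIC should be documented". It also requires, once CIC has begun, that "the status of CIC use should be documented in the subject record at each visit".

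No section of either document says what length to assign to an episode that has not ended.

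**The concern.** A length needs a stop date, and a subject who is still catheterising does not have one. If such subjects are left out of the length summary, they are left out because their episode has not ended, so the omission falls preferentially on long episodes. The summary would then describe resolved episodes while being labelled as all CIC use.

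Open episodes are foreseeable. Protocol 8.4.5 lets the investigator continue CIC even when the cessation criteria are met. Under the Schedule of Assessments, Weeks 36 and 48 are telephone or virtual visits, and subjects who withdraw early do not have them. CIC in use at withdrawal or at Week 24 may therefore never acquire a recorded stop date.

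The stake is a descriptive safety figure. Urinary retention needing catheterisation is an adverse event of special interest (Protocol 8.5.6), and Table 14.3.8 is the only planned summary of how long CIC lasts. With about 26 subjects planned per active arm, users may be few, and one omitted subject could change the line.

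**Working it through.** The plan states no CIC rate or duration, so there is no figure of its own to reproduce. The check has two parts.

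**1. What the rules give for an open episode.**

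- Formula (SAP 4.3.4): later date − earlier date + 1.
- Earlier date: CIC start, recorded.
- Later date: CIC stop, which does not exist while use continues (Protocol 8.4.5).
- Substitution: SAP 7.8 imputes none, the SAP 4.2.3 partial-date rules do not reach CIC, and the general rule there is observed values only.
- Result: no length can be computed.

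For a subject with one closed and one open episode, the summing rule gives either a missing total or the closed episode alone. The SAP does not say which. The first drops her and the second understates her use.

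**2. How much it could matter. All CIC durations below are assumed.**

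*Small example.* Four users in an arm. Three stop after 14, 21 and 28 days. One starts on Day 15 and is still on CIC at last contact. Day 169 and Day 337 are the Week 24 and Week 48 target days in SAP 4.2.4.

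- As written: n = 3, mean (14 + 21 + 28)/3 = 21.0, median 21.0, maximum 28.
- Open episode counted to Day 169: 169 − 15 + 1 = 155; n = 4, mean (63 + 155)/4 = 54.5.
- Open episode counted to Day 337: 337 − 15 + 1 = 323; n = 4, mean (63 + 323)/4 = 96.5.
- The median is (21 + 28)/2 = 24.5 in both cases.

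The mean and maximum move a great deal, and the median only from 21.0 to 24.5. Both means that include the open episode are lower bounds.

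*Range under an exponential duration.* Let m be the true mean, with CIC starting on Day 15 and follow-up to Day 337, so L = 323.

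- Share still open = exp(−L/m).
- Mean of closed episodes = m − L·exp(−L/m)/(1 − exp(−L/m)).
- Mean with open episodes cut at L = m·(1 − exp(−L/m)).

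| True mean (days) | Share open | Closed episodes only | Open episodes cut at last contact |
|---|---|---|---|
| 30 | 0.0% | 30.0 | 30.0 |
| 60 | 0.5% | 58.5 | 59.7 |
| 120 | 6.8% | 96.5 | 111.9 |
| 240 | 26.0% | 126.3 | 177.5 |
| 480 | 51.0% | 143.5 | 235.1 |

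For m = 240: exp(−323/240) = 0.260, and 240 − 323 × 0.260/0.740 is about 126.3 with unrounded values. The bias is downward throughout. It is negligible when nearly every episode closes and large when many stay open. Cutting at last contact reduces the bias but does not remove it, which is why the number still open has to be shown as well.

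**The case against.** A reader might infer that the SAP expressly excludes subjects with ongoing CIC. It does not. The no-imputation sentence could mean only that the partial-date conventions for adverse events and medications do not extend to CIC. Counting an open episode to last contact is censoring, which SAP 7.8 neither prescribes nor prohibits. This stands as a limit on the wording: the exclusion is inferred from several rules read together. It does not remove the problem, because on that reading the rule for ongoing use is still missing.

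A reader might also infer that these subjects disappear from the safety reporting. The documents do not support that. They stay in the time-to-start summary and the CIC listing. Starting CIC for elevated residual volume triggers a urinary-retention event, which is tabulated and listed as an event of special interest, and the overall adverse event listing carries start and stop dates (SAP 7.2). Residual volume is summarised by visit and as maximum and last post-baseline value, with a category at 350 mL and above (SAP 7.7). SAP 4.2.2 also reports n, so an n for length below the n for time to start would be visible. All of this stands. What none of it supplies is the length of use, or the reason for a smaller n.

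Thirdly, the durations above are invented, and the mean is the statistic most sensitive to one long episode. Protocol 2.3.2 reports no urinary retention at doses up to 24 mg in earlier work, although that does not cover 48 mg. This stands: nothing in the documents shows that open episodes will be common, or more common in one arm.

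Finally, Kaplan-Meier estimation on a handful of users would be a matter of preference. That is accepted.

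**Conclusion.** The point holds in a limited form. Followed as written, SAP 7.8 with 4.3.4 and 4.2.3 leaves a subject with ongoing CIC without a length, so the length-of-use line understates duration if at least one subject is still catheterising at withdrawal or last contact. If every user stops and has a recorded stop date, there is no error.

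The direction follows from the rules, but the size cannot be derived from the documents. The figures in the working show only how the result depends on the share of open episodes. They should not be read as forecasts, nor as evidence that retention will look short-lived overall or that one arm will be flattered more than another. The summary is descriptive and no efficacy result is affected. It merits correction because this is the only planned summary of CIC duration and the correction is small.

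**What to change.** In SAP 7.8:

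- State that a CIC episode with no stop date is counted from its start to the last contact with documented use, and is flagged as censored and shown as '> x days'.
- Apply the same rule when a closed and an open episode are summed, and flag the total.
- In Table 14.3.8, add by arm the number and percent of CIC users still on CIC at last contact.
- Leave a Kaplan-Meier median as optional, only if there are enough users.

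The cost is one derivation rule and one table row. No new assessment should be needed, because Protocol 8.4.5 already requires use or nonuse to be documented at each visit. It places this in the subject record, however, and the Schedule of Assessments has no CIC row, so the sponsor should confirm that the last date of documented use reaches the database. The drawback is that lengths reported for open episodes are lower bounds, so means that include them must be labelled as such.
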